12.0 Data Management

Participants' privacy will be protected via alpha-numeric coding of the data once obtained. Names of participants will not be entered in the database, instead they will be identified by assigned code. Information linking the code to the participant will be kept securely by the PI. There will be no link to the participant after study completion. The consent forms, which are the possible way to breach confidentiality, will be stored in the PI's office as well in a secure location. All clinical data pertaining to the study will be stored online in REDCap.

13.0 Provisions to Monitor the Data to Ensure the Safety of Subjects (if applicable)

Adverse event (AE) reporting Adverse events anticipated in this study that involves a fasting blood draw and potential side effects of fenofibrate (for example myalgias, elevation of liver enzymes) are few. Risks associated with drawing blood from the arm include momentary discomfort and/or bruising. Infection, excess bleeding, clotting, or fainting is possible, although unlikely.

Risk minimization These risks will be minimized by allowing only well-trained clinical research staff of the SCTR NEXUS facility to perform study procedures and testing according to standard practice, and by making sure study participants clearly understand study procedures before and during the study protocol.

The blood draw will be performed with the subject resting and recumbent. Adequate rest time will be provided after the blood draw to avoid a hypotensive response. Breakfast will be provided at the end of blood draw. Participants will be instructed to report any concerning symptoms. If necessary, adverse events will be reported to the PI and the IRB. Unanticipated non-serious adverse events must be reported from the investigator to the IRB no later than 10 working days after the event or notification to the investigator that the event has occurred, and serious adverse events will be reported within 24 per MUSC IRB guidelines. In absence of moderate or serious adverse events, reports of study progress will be submitted to the IRB for review on an annual basis.

The potential benefits of the research, which may include lowering of cholesterol and the identification of major new risk factors for complications of diabetes, are considered to outweigh the minimal risks involved.

Monitoring of Study Implementation and Progress Periodic assessments will be performed to assess recruitment and retention of study participants, data quality, and risk-benefit ratio. The recruitment goal for this study is to recruit over the period of 6 months 40 (20 males and 20 females) type 2 diabetic participants with elevated triglycerides. Data checks will be performed by Drs. [name] and [name]. If additional information regarding the study's risk-benefit ratio becomes available, the PI will be responsible for notifying the IRB, sponsor, and study participants, as indicated.

A record will be kept of patients who were considered for enrollment but not enrolled e.g., patient screening log to establish that the participant population was selected without bias.

14.0 Withdrawal of Subjects (if applicable)

Participants may be discontinued from study treatment at any time. Specific reasons for discontinuation from this study are:

- Study treatment not tolerated and raising safety concerns. Non-toleration of study drug could include any symptoms of myalgia or at the investigator's discretion.
- Voluntary discontinuation by the participant who is at any time free to discontinue their participation in the study, without prejudice to further treatment.
- Safety reasons as judged by the investigator.
- Occurrence of an adverse event, which in the opinion of the investigator warrants the participant's discontinuation.
- If at any time the participant experiences unexplained muscle pain, tenderness or weakness, study medication should be discontinued.
- Participant lost to follow-up.
- Pregnancy.
- Deterioration in the participant's condition which in the opinion of the investigator warrants study medication withdrawal.

Participants who discontinue will be asked the reason(s) for their discontinuation and the presence of any adverse events. The participant must return all unused investigational products to the investigator. The number of encapsulated tablets returned must be checked against the number dispensed to determine participant compliance.

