10.0 Study Design / Methods

Regularly scheduled Endocrinology clinic visit:

- If participants qualify and agree to participate, they will be provided an informed consent form, and a HIPAA form and provided the opportunity to sign agreement to participate.
- Visit one will then be scheduled for participants at the SCTR NEXUS clinic by the research coordinator.
- Participants will be instructed on fasting protocol following consent process and prior to visit one.

Visit 1:

[figure not shown]
- Upon arrival at the SCTR NEXUS clinic, a physical examination will be performed by either the PI or co-investigators. Clinical data will be recorded to include demographic information, diabetes complication status and medications, and anthropometric information.
- Women of childbearing potential will have urine β -HCG measured (+pregnancy outcome is criteria for exclusion) and will be required to use the following as acceptable methods for birth control throughout the study: 1) barrier methods including male and female condoms, diaphragm, cervical cap and contraceptive sponge, 2) hormonal methods including birth control pills, vaginal ring (NuvaRing), contraceptive implant (Nexplanon), contraceptive injection (Depo-Provera) and birth control patch, 3) intrauterine devices (IUDs) such as the copper IUD (ParaGard) and the hormonal IUD (Mirena, Skyla, Kyleena, others), 4) sterilization to include tubal ligation or the Essure system for women, and vasectomy for men, or 5) avoiding sexual activity that could cause you to become pregnant.
- Fasting blood (80ml) will be obtained for baseline labs (BUN, Cr, urine microalbumin, LFTs, CPK, Lipid Profile, HbA1c, TSH, C-peptide) and processed to yield heparin, EDTA, and citrate-plasma, serum, and pellets (sufficient for all planned analyses). A timed morning urine sample will be collected with the volume recorded. Samples will be stored in ultra-low freezers for proteomics and subsequent confirmatory assays (by ELISA).
- Participants will then be given the study medication (160 mg fenofibrate to be taken orally daily for six weeks) by the research physician. As well, they will receive instruction on possible side effects and proper protocol for reporting unexpected symptoms.
- Following venipuncture, participants will be given a choice of breakfast foods from which to choose by the IRB approved personnel and a place to eat.
- Participants will receive a gift card at the completion of visit one in the amount of \$25.

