- Participants will be scheduled for visit 2 in six weeks.

Visit 2:

- Upon arrival at the SCTR NEXUS clinic, a physical examination will be performed by either the PI or co-investigators. Clinical data will be recorded to include demographic information, and medications, and anthropometric information.
- Fasting blood (80ml) will be obtained for follow-up labs (BUN, Cr, urine microalbumin, LFTs, CPK, Lipid Profile, HbA1c, TSH, C-peptide) and processed to yield heparin,

EDTA, and citrate-plasma, serum, and pellets (sufficient for all planned analyses). A timed morning urine sample will be collected with the volume recorded. Samples will be stored in ultra-low freezers for proteomics and subsequent confirmatory assays (by ELISA).

- Participants will then undergo an assessment of adverse events and study drug compliance, which will be determined by pill count.
- Following venipuncture, participants will be given a choice of breakfast foods from which to choose by the IRB approved personnel and a place to eat.
- Participants will receive a gift card at the completion of visit two in the amount of \$25.
- The plasma proteomic signature will be generated by LC-MS/MS (n=80 proteomes) of each subject before and after fenofibrate treatment. Bioinformatic approaches will then be employed based on geneset enrichment analysis to identify the biological processes/signaling networks impacted by treatment.

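### Does Section 14 need to separate stopping the study drug from leaving the study, so that the second sample is secured?

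*Protocol*

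**What the plan says.** Section 14.0 of the Protocol opens: "Participants may be discontinued from study treatment at any time. Specific reasons for discontinuation from this study are". The reasons listed under that lead-in are of two kinds.

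- **Worded as stopping the drug.** One item reads "If at any time the participant experiences unexplained muscle pain, tenderness or weakness, study medication should be discontinued". The last item, on deterioration, also speaks of withdrawing medication.
- **Worded as leaving the study.** One item reads "Voluntary discontinuation by the participant who is at any time free to discontinue their participation in the study". Loss to follow-up belongs here too.

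Muscle symptoms appear twice: in the item just quoted and under intolerance, where "Non-toleration of study drug could include any symptoms of myalgia or at the investigator's discretion".

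The section then says what happens next: "Participants who discontinue will be asked the reason(s) for their discontinuation and the presence of any adverse events". Unused product is returned, and "The number of encapsulated tablets returned must be checked against the number dispensed to determine participant compliance". A second blood or urine sample is not mentioned.

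Section 10.0 sets the course ("160 mg fenofibrate to be taken orally daily for six weeks") and the visit ("Participants will be scheduled for visit 2 in six weeks"), and has compliance assessed at Visit 2 by counting tablets. Section 1.0 describes samples taken directly before and after treatment. Section 17.0 requires medication-related procedures to be entered on a drug accountability form.

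**The concern.** There is one treated arm and no control, so each participant's before/after pair carries all the information on drug effect. The wording of Section 14.0 allows two readings for someone who stops the drug but is willing to continue.

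- **Stopping the drug ends participation.** No second sample is drawn, and the pairs under-represent people who did not tolerate fenofibrate.
- **Only the drug stops.** Visit 2 stays at six weeks, and the second sample may come from someone who has been off drug for some time. That sits badly with the description in Section 1.0 of samples taken directly after treatment.

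The tablet count does not resolve the second case, because it gives the number of doses not taken and no dates. Nor could a later analysis plan supply a sample that was never drawn. The stored samples are also meant for future research, so an off-drug sample labelled as after treatment could mislead later users.

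**Working it through.** **The plan's own figure.** Section 6.0 gives 40 participants and Section 10.0 gives 80 proteomes. 40 × 2 = 80, which agrees. The figure has no allowance for a missing second sample.

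**Precision if early stoppers give no second sample.** The Protocol states no dropout rate, so the rates below are assumptions. With n pairs, the standard error of a mean change is proportional to 1/√n, so the relative rise is √(40/n) − 1.

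| Assumed loss | Pairs left | Proteomes | Rise in standard error |
|---|---|---|---|
| 5% (2 of 40) | 38 | 78 | √(40/38) − 1 = 2.6% |
| 10% (4 of 40) | 36 | 76 | √(40/36) − 1 = 5.4% |
| 20% (8 of 40) | 32 | 72 | √(40/32) − 1 = 11.8% |

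These losses include people who withdraw voluntarily or cannot be traced. They would be lost under any wording, so the share due to Section 14.0 is smaller than the table shows.

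**What an early-draw rule would recover.** At 5% to 10% loss, at most 2 to 4 early pairs would be gained. Their exposure would be shorter and variable. An analysis of six-week completers would keep 38 or 36 pairs, so the 2.6% and 5.4% would remain.

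**What the tablet count can show.** Six weeks of daily dosing is 6 × 7 = 42 doses. The number dispensed is not stated, so 42 is assumed. If r tablets come back, the last dose may fall on any day from 42 − r to 42, and the gap to day 42 is 0 to r days. For r = 7 that is 0 to 7 days, and for r = 21 it is 0 to 21 days. The count alone cannot date the last dose. This is true of any tablet count and is not peculiar to Section 14.0.

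**The texts side by side.** The heading of Section 14.0 concerns withdrawal of subjects. One lead-in, phrased as leaving the study, governs every listed reason. The closing steps (reasons, adverse events, tablet return) are those of an exit. Both muscle-symptom items lead to stopping the drug, so they do not conflict on that action. Section 1.0 describes a cohort treated for six weeks and sampled before and after. Taken together, these point to the first reading: someone who stops the drug leaves, and the comparison is among those who complete the course. On that reading, the different timings for an early stopper in Sections 1.0 and 10.0 do not arise.

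**Whether the stop date is lost.** When the investigator stops the drug, the investigator knows the date. When the participant stops, Section 14.0 already has staff ask why, and the date can be asked with it. The accountability form in Section 17.0 is a natural place to write it, although the Protocol does not list that field.

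**The case for a change.** The strongest case for a change is that sample collection belongs in the protocol. An analysis plan can choose among samples but cannot create them, and links to identity are destroyed at the end of the study, so a gap then could not be closed. Separating the two kinds of discontinuation and recording the date of last dose would cost a few words and one data item. The important loss would be selective: those who drop out may be those who tolerate the drug least, and a standard-error figure does not measure that.

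Part of this stands. The terms are used loosely, no section expressly covers the willing participant who stops early, and the tablet count does not date the last dose. Selection is possible in principle.

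It does not carry a change to the plan. Section 13.0 expects few adverse events. Section 4.0 fixes no endpoint, and Section 5.0 calls the work discovery research, so no decision is shown to turn on two to four people. Early pairs would not repair selection in a six-week comparison either, because they measure a different exposure.

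The early draw also has a price. If only the drug has stopped, it moves the visit that carries the follow-up liver, CPK and creatinine tests. If the participant has left, it adds a fasting visit and an 80 ml draw, although the total stays at the planned 2 × 80 = 160 ml. Which of these to accept is for the sponsor to weigh, and the statistics do not settle it.

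**Conclusion.** No change to the plan follows. The observation about wording is correct, but it amounts to an unstated policy for an uncommon case, in a section whose natural reading already supplies one: stopping the drug ends participation. The before/after comparison among six-week completers remains sound as written.

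The size is small. If 5% to 10% were lost, the standard error would rise by 2.6% to 5.4%, and an early-draw rule would leave that rise in place while adding at most 2 to 4 descriptive pairs. The conclusion rests on three things: the assumed loss rates, since the Protocol gives none; the reading of Section 14.0 as study exit, which its heading, lead-in and closing steps support but no sentence states outright; and ordinary practice in noting when a participant stopped. If stops were much more common, say 20%, the rise would be 11.8% and selection would deserve more weight, but nothing in the Protocol points to that rate.

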15.0 Risks to Subjects

Potential risks are low and include:

- Research records will be confidential. There is a small risk of loss of confidentiality, but records will be stored, locked in the PI's office as a means of preventing this loss of confidentiality.
- Hazards of venipuncture: pain, bruising, inflammation or clot formation, syncope. Procedures for minimizing potential risks include the use of aseptic techniques for venipuncture, and drawing blood with subjects in the recumbent position. Subjects will be provided explanation in advance about laboratory test procedures to be performed. The subject's results will be known only to the investigators.
- Fenofibrate use has been associated with an increased risk of muscle pain, abnormal results in tests of liver function and allergic reaction. Participants will be instructed on risks and provided protocol for reporting with medication administration.

16.0 Potential Benefits to Subjects or Others

Fenofibrate lowers triglyceride levels, and has been found to confer unrelated and unexpected therapeutic benefit on diabetic retinopathy in two large clinical trials on type 2 diabetic subjects. Additional clinical data suggest that fenofibrate has beneficial effects in diabetic nephropathy, limb ischemia, diabetic neuropathy, hepatic fibrosis, cancer, and other conditions. However, these studies involve longer-term use of the drug, and there is no evidence that short-term use, as in the present study, will confer any benefit.

17.0 Drugs or Devices (if applicable)

All study medication will be procured from MUSC's Pharmacy Distribution Center. It will be labeled, in its original packaging according to FDA standards, by the research coordinator. Medications will be stored securely at room temperature in the [name] lab in a locked cabinet. All medications will be dispensed to participants by an IRB-approved,

licensed practitioner. All medication-related procedures will be recorded on a drug accountability form.

References

2. ACCORD Study Group; ACCORD Eye Study Group, Chew EY, Ambrosius WT, Davis MD, Danis RP, Gangaputra S, Greven CM, Hubbard L, Esser BA, Lovato JF, Perdue LH, Goff DC Jr, Cushman WC, Ginsberg HN, Elam MB, Genuth S, Gerstein HC, Schubart U, Fine LJ. (2010) Effects of medical therapies on retinopathy progression in type 2 diabetes. *N Engl J Med.* **363:** 233-244.
